## 2 PROTOCOL SYNOPSIS

Title	A Phase 3b Open-label Study Evaluating the Safety of Elexacaftor/Tezacaftor/Ivacaftor Combination Therapy in Cystic Fibrosis Subjects
Brief Title	A Study Evaluating the Safety of Elexacaftor Combination Therapy
Clinical Phase and Clinical Study Type	Phase 3b, safety
Objectives	
Primary Objective
 
To evaluate the safety and tolerability of elexacaftor (VX-445; ELX)/tezacaftor (TEZ)/ivacaftor (IVA)

Endpoints	
Primary Endpoint
 
Safety and tolerability of ELX/TEZ/IVA based on adverse events (AEs), clinical laboratory values, ECGs, vital signs, and pulse oximetry

Number of Subjects	Up to approximately 158 subjects are expected to enroll in this open-label study
Study Population	Male and female cystic fibrosis (CF) subjects with an F/F mutation who are 12 years of age or older
Investigational Drug	
Active substance: ELX (VX-445)/TEZ (VX-661)/IVA (VX-770)
 
Activity: CFTR correctors (ELX and TEZ) and potentiator (IVA); increased Cl secretion
 
Strength and route of administration: 100 mg/50 mg/75 mg, oral
 
Active substance: IVA (VX-770)
 
Activity: CFTR potentiator; increased Cl secretion
 
Strength and route of administration: 150 mg, oral

Study Duration	For subjects who participate in both Parts A and B, the total study duration is approximately 148 weeks (from the first dose of study drug in this study), including a treatment duration of 144 weeks (Treatment Periods of 48 weeks in Part A and 96 weeks in Part B), and a 4-week Safety Follow-up Visit.

**Study Design** This is a Phase 3b, 2-part, multicenter, open-label study for subjects who complete a parent study and meet eligibility criteria. A schematic of the study design is shown in Figure 2-1.

All subjects in Parts A and B will receive the triple combination of ELX 200 mg qd/TEZ 100 mg qd/IVA 150 mg q12h. Subjects who complete Part A will have the opportunity to participate in Part B for an additional 96 weeks. For all subjects, a Safety Follow-up Visit is scheduled to occur 28 ( $\pm$  7) days after the last dose of study drug in Parts A and B.

**Figure 2-1 VX19-445-115 Study Design**

ELX: elexacaftor; IVA: ivacaftor; q12h: every 12 hours; qd: once daily;  
TEZ: tezacaftor

Note: Figure is not drawn to scale.

a All subjects will receive ELX 200 mg qd/TEZ 100 mg qd/IVA 150 mg q12h.

b Subjects whose Part B Day 1 is on the same day or within 1 calendar day as the Part A Week 48 Visit do NOT have to repeat any Part B Day 1 assessments that were specified to be performed at the Part A Week 48 Visit. Subjects whose Part B Day 1 is more than 1 calendar day after Part A Week 48 Visit must complete all assessments specified for the Part A Week 48 AND Part B Day 1 Visits.

For treatment continuity in regions where ELX/TEZ/IVA is not commercially available, an option to return to this study will be offered to subjects who depart this study to enroll in another Vertex study of investigational CFTR modulators (hereafter referred to as “another qualified Vertex study”) based on the following:

- Subjects receive open-label ELX/TEZ/IVA during the other study’s Run-in Period but have not received study drug in the Treatment Period of the other study, and
- Meet all eligibility criteria for this study at their Returning Visit

Subjects who resume participation in this study will resume treatment with study drug after completion of a Returning Visit. Resumption of participation in this study following departure to another qualified Vertex study will be permitted only once.

**Assessments** **Safety:** AEs, clinical laboratory assessments, ECGs, vital signs, height (for subjects  $\leq$ 21 years of age on the date of informed consent in a parent study), weight, pulse oximetry, physical examinations (PE), and ophthalmologic examinations (for subjects  $<$ 18 years of age on the date of informed consent in a parent study).

**Statistical Analyses** The safety analyses will be performed for subjects who receive at least 1 dose of study drug in this study. The safety analyses will be descriptive only.

### **3 SCHEDULE OF ASSESSMENTS**

The schedules of assessments for Parts A and B are in Table 3-1 and Table 3-2, respectively. All visits will be scheduled relative to the Part A Day 1 Visit in this study.

Assessments may be performed in any order when more than 1 assessment is required at a particular time point. All assessments should be performed before study drug dosing (Section 9.6.1), unless noted otherwise.

Subjects who depart this study to enroll in another qualified Vertex study, and who meet the eligibility criteria in Section 8, may resume participation in this study only once.

**3.1 Part A**

Event/Assessment a	Treatment Period Part A					Part A ETT Visit/ Departing Visit b	Part A Safety Follow-up Visit (28 ± 7 Days After Last Dose) c	Comments
	Day 1/ Returning Visit d	Day 15 (± 3 Days)	Weeks 4, 12, 24, 36 (± 5 Days)	Weeks 8, 16, 20, 28, 32, 40, 44 (± 5 Days)	Week 48 (± 5 Days) e			
Clinic visit	X	X	X		X	X	X	
Telephone contact				X				Results of a home urine pregnancy test will be reported to the site by telephone (Section 11.2.2)
ICF and assent (when applicable)	X							ICF and assent are not required for Returning Visit
Inclusion and exclusion criteria confirmation	X							Section 8
Height and weight	X		X		X		X	Measured with shoes off. For subjects whose date of informed consent occurs after their 21 st birthday, height will not be collected (Section 11.2.4).

- a All assessments should be performed before study drug dosing, unless noted otherwise.
- b If the subject prematurely discontinues study drug treatment, an ETT Visit should be scheduled as soon as possible after the decision to discontinue treatment (Section 9.1.3). If the subject prematurely discontinues treatment to participate in another qualified Vertex study, the Departing Visit should be completed before or on the same day as the visit at which they receive the first dose of study drug in the Run-in Period of the other qualified Vertex study. The Safety Follow-up Visit will not be required if the subject enrolls in the other qualified Vertex study within 28 days of the last dose of study drug in this study.
- c The Safety Follow-up Visit is required for all subjects, unless otherwise specified (Section 9.1.2). For subjects who complete an ETT Visit 3 weeks or later following the last dose of study drug, the ETT Visit will replace the Safety Follow-up Visit.
- d The Day 1 Visit should occur on the same day as the last scheduled visit in the Treatment Period of a parent study (Section 9.1.1). Assessments at the Day 1 Visit must be performed before study drug dosing. Subjects who resume participation in this study after participation in another qualified Vertex study will complete the Returning Visit (which will consist of all assessments in the Day 1 Visit) and will resume treatment with ELX/TEZ/IVA after completion of the Returning Visit. Study visit numbering for returning subjects will resume based on the last study visit before the Departing Visit in this study. If the Returning Visit window coincides with a scheduled visit in this study, only the Returning Visit assessments will be completed. Subjects who resume participation but have their first dose of study drug in this study delayed will repeat the safety assessments specified to be performed at the Returning Visit before receiving their first dose of study drug.
- e Subjects whose Part B Day 1 is on the same day or within 1 calendar day as the Part A Week 48 Visit do NOT have to repeat any Part B Day 1 assessments that were specified to be performed at the Part A Week 48 Visit. Subjects whose Part B Day 1 is more than 1 calendar day after Part A Week 48 Visit must complete all assessments specified for the Part A Week 48 AND Part B Day 1 Visits.

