#### **9.1.2 Safety Follow-up**

The Safety Follow-up Visit is scheduled to occur 28 ( $\pm$  7) days after the last dose of study drug in Parts A and B. The Safety Follow-up Visit assessments are listed in Table 3-1 and Table 3-2, respectively.

The Safety Follow-up Visit is required for all subjects. However, subjects in Parts A and B who transition within 28 days of the last dose of study drug to either:

- a commercially available Vertex CFTR modulator regimen
- managed access program-supplied Vertex CFTR modulator regimen
- or, to another Part of the current study or another qualified Vertex study

will complete the respective Part A Week 48 or Part B Week 96 Visit. If the transition occurs before the Part A Week 48 Visit or Part B Week 96 Visit, then subjects will complete the Early Termination of Treatment (ETT) Visit. In these cases, the Part A Week 48/Part B Week 96 Visit or the ETT Visit, whichever is applicable, will replace the Safety Follow-up Visit.

For subjects who complete an ETT Visit 3 weeks or later following the last dose of study drug, the ETT Visit will replace the Safety Follow-up Visit (Section 9.1.3).

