### **11.2.4 Height and Weight**

Height and weight will be measured with shoes off, as applicable.

- Height will not be collected for subjects whose date of informed consent in Part A occurs after their 21st birthday.
- Height will be collected through the first visit after the subject's 21st birthday for subjects whose date of informed consent in Part A occurs on or before their 21st birthday; height will not be collected at subsequent visits.

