9.1.3.4 Vital Signs

For the vital signs measurements during the TE period for Part A, the observed values and change from baseline values will be summarized at each visit. The following vital signs parameters will be summarized: BMI (kg/m²), weight (kg), systolic and diastolic blood pressure (mm Hg), body temperature (°C), pulse rate (beats per minute), and respiratory rate (breaths per minute).

The number and percentage of subjects meeting at least 1 threshold analysis criterion event during the TE period for Part A will be summarized. The threshold analysis criteria are provided in Section 12.4.

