DBP increased	>90 mmHg >100 mmHg >5 mmHg increase from baseline >10 mmHg increase from baseline	
	>90 mmHg and >5 mmHg increase from baseline >90 mmHg and >10 mmHg increase from baseline >100 mmHg and >5 mmHg increase from baseline >100 mmHg and >10 mmHg increase from baseline	
DBP decreased	<60 mmHg <45 mmHg >5 mmHg decrease from baseline >10 mmHg decrease from baseline	
	<60 mmHg and >5 mmHg decrease from baseline <60 mmHg and >10 mmHg decrease from baseline <45 mmHg and >5 mmHg decrease from baseline <45 mmHg and >10 mmHg decrease from baseline	
Weight	Weight gain ≥5 % increase from baseline ≥10 % increase from baseline ≥ 20% increase from baseline	CTCAE grade 1-3
	Weight loss ≥5 % decrease from baseline ≥10 % decrease from baseline ≥ 20% decrease from baseline	CTCAE grade 1-3

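### Weight is not scheduled at the ETT/Departing Visit in either Part, so weight-threshold events near discontinuation can be missed in early stoppers

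*Protocol*

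**What the plan says.** **Schedule.** In Table 3-1 the "Height and weight" row is marked at Day 1/Returning, Weeks 4, 12, 24 and 36, Week 48 and Safety Follow-up. In Table 3-2 it is marked at Day 1/Returning, every 12 weeks from Week 12 to Week 84, Week 96 and Safety Follow-up. In both tables the ETT/Departing cell is blank.

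**Text.** Protocol Section 11.2.4 says "Height and weight will be measured with shoes off, as applicable" and gives age rules for height. It adds no visit.

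**Replacement of Safety Follow-up.** There are three routes.
- Under Section 9.1.2, for subjects who move within 28 days of the last dose to a commercial or managed-access regimen, to the other Part or to another qualified study, "the Part A Week 48/Part B Week 96 Visit or the ETT Visit, whichever is applicable, will replace the Safety Follow-up Visit". The ETT Visit applies when the move comes before Week 48 or Week 96.
- Under Table 3-1 footnote c, "For subjects who complete an ETT Visit 3 weeks or later following the last dose of study drug, the ETT Visit will replace" Safety Follow-up.
- Under Table 3-1 footnote b, "The Safety Follow-up Visit will not be required if the subject enrolls in the other qualified Vertex study within 28 days" of the last dose. Table 3-2 has the same two footnotes.

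**Analysis.** SAP Section 9.1.3.4 treats weight and BMI as vital-sign parameters and says "The number and percentage of subjects meeting at least 1 threshold analysis criterion event during the TE period for Part A will be summarized". Table 12-6 sets the weight criteria, for example "Weight loss ≥5 % decrease from baseline", with 10% and 20% steps and matching criteria for gain. SAP Section 9.2.3 repeats the safety analyses for Part B.

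**The concern.** The ETT Visit is the last clinic visit for some subjects who leave treatment early, and it can formally take the place of Safety Follow-up. Weight is an expected assessment at the visit being replaced but not at its replacement. Protocol Section 9.3.3, on the rationale for assessments, gives no reason for the difference, so it looks like an oversight.

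At stake is even ascertainment of a planned safety count. A completer is weighed at Week 48 or Week 96, and the schedules place the last dose on the evening before. An early stopper has no scheduled weight at the corresponding point. A weight change that crosses a threshold after the last scheduled weight can go unrecorded, and the subject then stays in the Safety Set denominator as a non-event.

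**Working it through.** The plan gives no figure to reproduce: the enrolment of about 158 is an expectation, and all analyses are descriptive. The check has four steps.

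**1. Is the blank cell real?** Reading the rows by column, the number of cells matches the header in both tables, and the gap appears in both tables independently, so a reading error is unlikely. Compared with the neighbouring columns:
- Everything marked at Week 48 or Week 96 is also marked at ETT/Departing, except height and weight. That covers clinic visit, ophthalmologic examination, physical examination, pregnancy test, ECG, vital signs, pulse oximetry, urinalysis, hematology, coagulation, chemistry and drug count.
- Everything marked at Safety Follow-up is also marked at ETT/Departing, with the same single exception.

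**2. Does another assessment supply weight?** No. Section 11.2.3 defines vital signs as blood pressure, temperature, pulse rate and respiration rate, and the physical examination as a review of body systems. Neither includes weight.

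**3. How old can the last scheduled weight be at the stop?** The inputs are the SAP Table 12-1 target days and the ±5-day visit windows in Tables 3-1 and 3-2.
- Part A weights fall on days 1, 29, 85, 169, 253 and 337. The intervals are 28, 56, 84, 84 and 84 days, so the longest is 84.
- Part B weights fall on day 1 and then every 84 days to day 673. That gives eight intervals of 84 days.
- If one visit is 5 days early and the next 5 days late, the longest interval is 84 + 5 + 5 = 94 days.
- If stops are spread evenly over the treatment period (an assumption), the mean age of the last weight is Σ(g²/2)/Σg, where g is the interval length. In Part A this is (28² + 56² + 3 × 84²)/(2 × 336) = 25,088/672 = 37.3 days. In Part B it is 84/2 = 42 days.
- A subject who stops before Week 4 of Part A, or before Week 12 of Part B, has only the Day 1 weight in that Part unless a Safety Follow-up Visit takes place.

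**4. Who is weighed after stopping, and does that weight count?** The TE Period ends 28 days after the last dose or at completion of participation, whichever is first (SAP 9.1.1 and 9.2.1).

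| Route | Scheduled weight after the stop | In the TE Period? |
|---|---|---|
| ETT Visit, then a separate Safety Follow-up | 28 ± 7 days, i.e. days 21 to 35 after the last dose | Days 21 to 28 yes; days 29 to 35 no |
| ETT Visit replaces Safety Follow-up (early transition, or ETT 3 weeks or later after the last dose) | None | Not applicable |
| Departing Visit, with enrolment in the other study within 28 days | None in this study, unless the subject comes back and is weighed at the Returning Visit | Only after return |

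Of the 15 days in the Safety Follow-up window, 8 (days 21 to 28) fall inside the TE Period and 7 (days 29 to 35) outside.

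**The case against.** The strongest reply is that the gap is narrow and the measure peripheral.

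- **Who is affected.** A reader might infer that subjects who stop for adverse events go unweighed. The documents do not support that. Section 9.1.3 asks for the ETT Visit as soon as possible after the decision to stop, and Section 9.1.2 then requires Safety Follow-up, where weight is marked. These subjects lose that weight only if the ETT Visit comes 3 weeks or later after the last dose. Those with no later weight also include subjects who change drug source or move to another study, who need not have stopped for toxicity. This stands.
- **What can still be counted.** A Safety Follow-up weight by day 28 is inside the TE Period, and the SAP visit-window rules accept unscheduled measurements. It would be wrong to say that an event in an early stopper cannot be counted. This stands too.
- **Departing subjects.** SAP Section 7.1 expects the depart-and-return option to apply only in Part B. A same-day Departing Visit follows the other study's schedule (Section 9.1.3), which may or may not include weight.
- **Importance.** Weight is not in the protocol's own vital-signs definition, and the analysis is single-arm and descriptive. Weight is, however, a listed safety assessment in the synopsis, and the SAP chose to place it among the vital signs with its own thresholds.
- **Use of an added weight.** The SAP has no ETT analysis visit, and a weight taken at an ETT Visit after day 28 would be outside the TE Period. The first part has little force: Table 12-1 assigns measurements by study day, so a Part A ETT weight on days 212 to 295, for example, would be eligible for the Week 36 summary as well as the threshold count.

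**Conclusion.** The point holds as an ascertainment gap in the schedule. Weight is the one measure (with height) missing at a visit that otherwise repeats the end-of-treatment and Safety Follow-up assessments, and the SAP counts weight-threshold events for both Parts.

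Where the ETT or Departing Visit replaces Safety Follow-up, the last scheduled weight can precede the stop by up to 84 days, or about 94 with visit windows. If stops are evenly spread, the average is 37 to 42 days. Other early stoppers are weighed only off drug, and that weight counts only if taken by day 28.

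A reader might go further and conclude that the threshold percentages are materially biased towards completers. The documents do not support this. They give neither the number of early stoppers nor the proportion on each route, and some late events remain countable. A missed event would lower the count, but the size of the effect is unknown. The matter is modest, and worth correcting because correction is cheap.

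**What to change.** Mark weight, and height where the Section 11.2.4 age rule applies, in the ETT/Departing column of Tables 3-1 and 3-2. Early stoppers who attend that visit would then have a weight there. Where the ETT Visit is prompt, that weight is close to the end of treatment. Where it is 3 weeks or more after the last dose, the weight is still off drug, and it enters the threshold count only if taken by day 28.

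The cost is one extra measurement at a clinic visit that already takes place, plus a minor protocol amendment with the approvals and submission described in Section 13.2.3.

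If data collection has ended, give beside the weight-threshold table, for each Part, the number of early stoppers without a weight at or near the end of treatment, and state the limitation. That needs only a count from existing data.

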**Table 3-1 Study VX19-445-115: Part A Treatment Period and Safety Follow-up Visit**

Event/Assessment a	Treatment Period Part A					Part A ETT Visit/ Departing Visit b	Part A Safety Follow-up Visit (28 ± 7 Days After Last Dose) c	Comments
	Day 1/ Returning Visit d	Day 15 (± 3 Days)	Weeks 4, 12, 24, 36 (± 5 Days)	Weeks 8, 16, 20, 28, 32, 40, 44 (± 5 Days)	Week 48 (± 5 Days) e			
Ophthalmologic examination					X	X		Subjects <18 years of age on the date of informed consent in a parent study and have completed at least 12 weeks of study drug treatment since their last ophthalmologic examination will have an ophthalmologic examination at the Part A Week 48 Visit or the Part A ETT Visit/ Departing Visit, whichever comes first. See Section 11.2.7 for acceptable assessment windows.
Complete physical examination (PE)	X				X	X		Symptom-directed PEs may be performed at any time if deemed necessary by the investigator (Section 11.2.3)
Pregnancy test	Urine		Urine	Urine	Serum	Serum	Serum	For all female subjects, at telephone contacts, a urine pregnancy test will be performed with a home kit provided by the study site. Results of the home pregnancy test will be reported to the site by telephone (Section 11.2.2).
Standard 12-lead ECG	X	X	Weeks 12, 24		X	X	X	Performed after subject has been at rest for at least 5 minutes (Sections 11.2.3, 11.2.5, and 11.2.6)
Vital signs	X	X	X		X	X	X	
Pulse oximetry	X	X	X		X	X	X	
Urinalysis	X				X	X	X	Section 11.2.2
Hematology	X	X	X		X	X	X	
Coagulation	X		Week 24		X	X	X	
Serum chemistry	X	X	X		X	X	X	
Study drug count	X	X	X		X	X		

Event/Assessment a	Treatment Period Part A					Part A ETT Visit/ Departing Visit b	Part A Safety Follow-up Visit (28 ± 7 Days After Last Dose) c	Comments
	Day 1/ Returning Visit d	Day 15 (± 3 Days)	Weeks 4, 12, 24, 36 (± 5 Days)	Weeks 8, 16, 20, 28, 32, 40, 44 (± 5 Days)	Week 48 (± 5 Days) e			
Study drug dosing	Day 1 through evening before Part A Week 48 Visit							Subjects on study drug interruption from a parent study or another qualified Vertex study may NOT begin dosing until they meet the resumption criteria in Section 9.8. The last dose of Part A should be taken on the evening before the Week 48 Visit. Refer to Section 9.6.1 for study drug administration details.
Medications review	Continuous from signing of the ICF through completion of study participation							Completion of study participation is defined in Section 9.1.5.
Treatments and procedures review	Continuous from signing of the ICF through completion of study participation							
AEs and SAEs	Continuous from signing of the ICF through completion of study participation							

AE: adverse event; ETT: early termination of treatment; ICF: informed consent form; PE: physical examination; SAE: serious adverse event

### 3.2 Part B

Event/Assessment a	Treatment Period Part B				Part B ETT Visit/ Departing Visit b	Part B Safety Follow-up Visit (28 ± 7 Days After Last Dose) c	Comments
	Day 1/ Returning Visit d	Weeks 12, 24, 36, 48, 60, 72, 84 (± 5 Days)	Weeks 4, 8, 16, 20, 28, 32, 40, 44, 52, 56, 64, 68, 76, 80, 88, 92 (± 5 Days)	Week 96 (± 5 Days)			
Clinic visit	X	X		X	X	X	
Telephone contact			X				Results of a home urine pregnancy test will be reported to the site by telephone (Section 11.2.2)
Part B ICF and assent (when applicable)	X						ICF and assent are not required for Returning Visit
Inclusion and exclusion criteria confirmation	X						Section 8
Height and weight	X	X		X		X	Measured with shoes off. For subjects whose date of informed consent occurs after their 21 st birthday, height will not be collected (Section 11.2.4).

a All assessments should be performed before study drug dosing, unless noted otherwise.

b If the subject prematurely discontinues study drug treatment, an ETT Visit should be scheduled as soon as possible after the decision to discontinue treatment (Section 9.1.3). If the subject prematurely discontinues treatment to participate in another qualified Vertex study, the Departing Visit should be completed before or on the same day as the visit at which they receive the first dose of study drug in the Run-in Period of the other qualified Vertex study. The Safety Follow-up Visit will not be required if the subject enrolls in the other qualified Vertex study within 28 days of the last dose of study drug in this study.

c The Safety Follow-up Visit is required for all subjects, unless otherwise specified. For subjects who complete an ETT Visit 3 weeks or later following the last dose of study drug, the ETT Visit will replace the Safety Follow-up Visit (Section 9.1.2).

d Subjects whose Part B Day 1 is on the same day or within 1 calendar day of the Part A Week 48 Visit do NOT have to repeat any Part B Day 1 assessments that were specified to be performed at the Part A Week 48 Visit. Subjects whose Part B Day 1 is more than 1 calendar day after the Part A Week 48 Visit must complete all assessments specified for the Part A Week 48 AND Part B Day 1 Visits. Subjects who resume participation in this study after participation in another qualified Vertex study will complete the Returning Visit (which will consist of all assessments in the Day 1 Visit) and will resume treatment with ELX/TEZ/IVA after completion of the Returning Visit. Study visit numbering for returning subjects will resume based on the last study visit before the Departing Visit in this study. If the Returning Visit window coincides with a scheduled visit in this study, only the Returning Visit assessments will be completed. Subjects who resume participation but have their first dose of study drug in this study delayed will repeat the safety assessments specified to be performed at the Returning Visit before receiving their first dose of study drug.

Event/Assessment a	Treatment Period Part B				Part B ETT Visit/ Departing Visit b	Part B Safety Follow-up Visit (28 ± 7 Days After Last Dose) c	Comments
	Day 1/ Returning Visit d	Weeks 12, 24, 36, 48, 60, 72, 84 (± 5 Days)	Weeks 4, 8, 16, 20, 28, 32, 40, 44, 52, 56, 64, 68, 76, 80, 88, 92 (± 5 Days)	Week 96 (± 5 Days)			
Ophthalmologic examination				X	X		Subjects <18 years of age on the date of informed consent in a parent study and who have completed at least 12 weeks of study drug treatment since their last ophthalmologic examination will have an ophthalmologic examination at the Part B Week 96 Visit or the Part B ETT Visit/Departing Visit, whichever comes first. See Section 11.2.7 for acceptable assessment windows.
Complete physical examination (PE)	X			X	X		Symptom-directed PEs may be performed at any time if deemed necessary by the investigator (Section 11.2.3)
Pregnancy test	Urine	Urine	Urine	Serum	Serum	Serum	For all female subjects, at telephone contacts, a urine pregnancy test will be performed with a home kit provided by the study site. Results of the home pregnancy test will be reported to the site by telephone (Section 11.2.2).
Standard 12-lead ECG	X	Week 24, 48		X	X	X	Section 11.2.2
Vital signs	X	X		X	X	X	
Pulse oximetry	X	X		X	X	X	
Urinalysis	X			X	X	X	
Hematology	X	X		X	X	X	
Coagulation	X	Week 48		X	X	X	
Serum chemistry	X	X		X	X	X	
Study drug count	X	X		X	X		

Table 3-2 Study VX19-445-115: Part B Treatment Period and Safety Follow-up Visit							
Event/Assessmenta	Treatment Period Part B				Part B ETT Visit/ Departing Visitb	Part B Safety Follow-up Visit (28 ± 7 Days After Last Dose)c	Comments
	Day 1/ Returning Visitd	Weeks 12, 24, 36, 48, 60, 72, 84 (± 5 Days)	Weeks 4, 8, 16, 20, 28, 32, 40, 44, 52, 56, 64, 68, 76, 80, 88, 92 (± 5 Days)	Week 96 (± 5 Days)			
Study drug dosing	Day 1 through evening before Part B Week 96 Visit						Subjects on study drug interruption from Part A or another qualified Vertex study may NOT begin dosing in Part B until they meet the resumption criteria in Section 9.8. The first dose of Part B will be given at the Day 1 Visit. Refer to Section 9.6.1 for study drug administration details.
Medications review	Continuous from signing of the Part B ICF through completion of study participation						Completion of study participation is defined in Section 9.1.5.
Treatments and procedures review	Continuous from signing of the Part B ICF through completion of study participation						
AEs and SAEs	Continuous from signing of the Part B ICF through completion of study participation						

AE: adverse event; ETT: early termination of treatment; ICF: informed consent form; PE: physical examination; SAE: serious adverse event

